No pause between Phase 2 and 3

Phase 3 Part

* Patients who culture convert will be treated for 12 months from 1st negative culture per treatment guidelines.
EOT = End-of-Therapy; LFU = Late Follow-up; OBR = Optimized Background Regimen; TBD = Final sample size to be confirmed based on Phase 2 Part data

The Phase 3 part of the study will test the superiority of epetraborole + OBR compared to placebo + OBR. In this part of the study, approximately 234 patients are planned to be randomized in a 2:1 ratio (156 patients receiving active epetraborole tablets and 78 patients receiving matching placebo tablets) using an IRT system and stratified by baseline use of ALIS and presence or absence of any fibrocavitary disease. The current symptom-based clinical response definition (using the MACrO₂ PRO) in Phase 3 is a placeholder to be verified after Phase 2 analyses, which will be based on data through Month 6. In addition, the Sponsor will determine if the sample size for Phase 3 should be adjusted and will confirm the Phase 3 epetraborole dosage regimen based on the observed plasma epetraborole exposure. Such changes will be addressed in a protocol amendment as appropriate. After the last patient in Phase 3 completes the Month 6 Visit, prespecified members of the Sponsor and non-Sponsor analysis teams will be unblinded to treatment assignment for Phase 3 data analyses; patients, Investigators, and other study staff will remain blinded to treatment assignment through the last

study visit (LFU) (see Study Blinding Plan). Initial Phase 3 data analyses will include a review of patient-reported clinical symptom responses, microbiological, safety, and PK data collected at multiple time points through Month 6. All patients in the study will receive a minimum of 6 months of blinded study drug treatment. At the Month 6 Visit, all available sputum culture results will be assessed by the Investigator to determine whether a patient is a converter or non-converter. Patients who are assessed as converters will continue taking blinded study drug for 12 months after the first month that defines sputum culture conversion, up to a maximum of 16 months. Patients who are assessed as non-converters will discontinue study drug at the Month 6 Visit. See additional details in [Section 3.1.1](#).

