3.1.1. Duration of Study Drug Administration and Study Participation

For the Phase 2 and Phase 3 parts of the study, the duration of study participation for each patient, not including Screening, will be up to approximately 19 months as described in [Section 3.1](#).

Each patient's duration of study participation will vary depending on the timing of microbiological sputum MAC culture conversion. To receive study drug beyond Month 6, a patient must have achieved a microbiological sputum MAC culture conversion.

All patients will receive a minimum of 6 months of blinded study drug treatment. At the Month 6 Visit, all available sputum culture results will be assessed by the Investigator to determine whether a patient is a converter or non-converter. A converter is defined as a patient who has 3 consecutive monthly MAC-negative sputum cultures at any time within the first 6 months of the study. A non-converter is a patient who does not have 3 consecutive monthly MAC-negative sputum cultures at any time within the first 6 months of the study.

Patients who are assessed as converters will continue taking blinded study drug for 12 months after the first month that defines sputum culture conversion, up to a maximum of 16 months. Patients who are assessed as non-converters will discontinue study drug at the Month 6 Visit. Patients who are discontinued from study drug at the Month 6 Visit will complete the EOT Visit at this time point, as well as the MACrO₂ and PGIS 1 week (+1 day) after their EOT Visit, and an LFU Visit 3 months (84 days \pm 14 days) after the last dose of study drug.

Because reporting of final respiratory culture and identification results may occur up to 8 weeks after specimen receipt at the regional or central microbiological laboratory, it is unlikely that the Month 5 culture results will be available at the Month 6 Visit. Patients who have negative culture results from Month 4 and no culture data available from Month 5 will be presumed to be converters and will continue blinded study drug at the Month 6 Visit. Such patients subsequently found to have positive cultures from the Month 5 and/or Month 6 visit must be discussed with the Medical Monitor for determination of continued study drug therapy beyond Month 6. Patients with *missing* sputum cultures from any visit prior to Month 6 should not be prematurely

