3.3.7 Study Drug Exposure

For each study phase, study drug exposure will be summarized in both a Month 6 analysis (all exposures from baseline through Month 6 visit) and final analysis (all exposures from baseline through EOT visit).

The following parameters will be calculated for the exposure data:

- Duration of the oral study drug treatment (days), defined as (the earliest date of Month 6 visit or early discontinuation – date of first treatment + 1) at Month 6 analysis and (date of last confirmed treatment – date of first treatment + 1) at final analysis (through EOT Visit for all patients).
- Compliance (%) for oral study drug will be calculated as $\frac{\text{actual number of tablets taken}}{\text{planned number of tablets}} \times 100$. Actual number of tablets taken = number of tablets dispensed – returned. Planned number of tablets will be calculated as a sum of all planned doses per intake for a patient.

Study drug compliance checks will be performed by study site or home health care staff by counting the number of remaining tablets in the study drug pill bottles at each study visit. The number of actual tablets taken will be calculated as number of tablets dispensed – number of tablets returned. If study drug is not returned for one or more bottles from a given study visit, the number of tablets expected and actual tablets taken for that visit will be excluded from the compliance calculation. The number of tablets expected will be calculated as the earliest date of Month 6 visit or early discontinuation – date of first dose of study drug +1, multiplied by 2 (i.e., the number of days study drug was expected to be taken x 2 tablets per day) for the Month 6 analysis, and date of last confirmed treatment – date of first dose of study drug +1, multiplied by 2 for the final analysis. Any protocol-directed interruption in study drug use due to adverse events or changes in local laboratory creatinine clearance as recorded in the clinical database will be accounted for by calculating each interruption duration (date of restart – date of last dose prior to interruption – 1)

multiplied by 2, and subtracting these from the denominator prior to calculating overall study drug compliance. Percent compliance to the study drug regimen will be summarized by treatment based on the Safety Population with descriptive statistics and with counts and percentages of patients with compliance in the following categories:

- <80%
- 80-100%
- >100%-120%
- >120%

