3.4 Efficacy Analysis

A primary objective of the Phase 2 part of the study is to assess MACrO₂ PRO instrument properties in determining symptom-based clinical response between baseline and Month 3 and baseline and Month 6. The primary objective of the Phase 3 part of the study is to determine if epetraborole + OBR is superior to placebo + OBR in clinical response between baseline and Month 6, as measured by the MACrO₂ PRO (pending verification from the Phase 2 part of the study). The other PRO instruments (QOL-B, NTM Symptoms Module, and SGRQ-C) will be incorporated as secondary objectives to assess for symptom/function-based clinical response to oral epetraborole compared to placebo.

As discussed in Section 2.2.6 ([Analysis Timing](#)), efficacy analyses will be performed in two stages for Phase 2. However, as the trial was prematurely terminated, only a single overall analysis stage will be performed for Phase 3 after final database lock and unblinding of Phase 3, at which time all efficacy and safety analyses will be performed. The initial stage of analyses will be conducted after the last patient in Phase 2 completes all assessments for the Month 6 visit (including Month 6 +1 week PRO assessments) and all data points though these time points have been entered and cleaned. This will be referred to as the Month 6 Analysis in Phase 2. All efficacy endpoints measured through Month 6 will be assessed at this time and considered final as part of this analysis. Any efficacy endpoint data collected at any visits beyond Month 6 (e.g., EOT, LFU) will not be summarized at the time of this analysis.

The second set of analyses will be conducted after all patients have completed all assessments through end of study and the database has been declared locked for each phase. This will be referred to as the End of

Study Analysis in each phase. All efficacy endpoints based on assessments collected beyond Month 6 in Phase 2 will be assessed at this time and considered final as part of this analysis.

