3.5 Safety Analysis

Safety data will be summarized by actual treatment received (and in total for selected analyses) as a primary endpoint in Phase 2 and a secondary endpoint in Phase 3 based on the Safety Population. All the analyses in this section will be run on the Safety Population of each study phase, and will be generated separately for all safety data collected through the Month 6 visit and again for all safety data collected through the end of study in Phase 2, while a single analysis of safety through the end of study will be generated for Phase 3. Safety data across the Phase 2 and 3 Safety populations will not be pooled as part of this analysis plan. No hypothesis testing will be performed; all analyses will be descriptive in nature.

Assessments of safety will include the following:

- Assessment of TEAEs;
- Changes from baseline and in laboratory tests (including chemistry, hematology, and urinalysis parameters), including shifts in severity grade or relative to normal ranges for selected laboratory parameters;
- Changes from baseline in vital signs; and
- Change from baseline in 12-lead ECG parameters.

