3.5.2 Clinical Laboratory Tests

Laboratory panels (hematology, chemistry, and urinalysis, with specific analytes for each panel listed in Protocol Appendix B) will be summarized by scheduled visit, along with changes from baseline to each scheduled post-baseline visit (Protocol Appendix A) for each test. All summary tables will be presented by treatment, for the Safety Population. Descriptive statistics will be provided for continuous variables; for categorical variables, number and percentage will be summarized. Only data from the central laboratory will be summarized. Separate tables will be presented for each laboratory panel. All clinical laboratory results will be displayed in original units as documented in SDTM.

Shift tables (number and percentage) will be provided by CTCAE 5.0 grades from baseline to the worst post-baseline assessment and will be summarized by treatment for selected laboratory tests (hemoglobin, white blood cell count, platelets, liver function tests [alanine aminotransferase, aspartate aminotransferase, and alkaline phosphatase], and serum creatinine). The worst post-baseline grade (for both directions if applicable) will be derived from all post-baseline visits including scheduled and unscheduled. Additionally, shift tables comparing shift from baseline to each scheduled post-baseline visit with respect to normal ranges (categorizations of low, normal, or high) will be presented for all laboratory parameters where normal ranges are provided.

Additional analysis of laboratory parameters (chemistry and hematology parameters will be summarized separately) will be performed in the Safety Population and will include frequencies for the following post-baseline values:

- Patients with at least a 2-grade increase in CTCAE toxicity grade from baseline in any parameter
- Patients with CTCAE toxicity grade ≥ 4 in any parameter

Analysis of patients with post-baseline aminotransferase elevations and total bilirubin by category will be performed for the following post-baseline values in the Safety Population and defined as:

- Alanine aminotransferase $>3x$, $>5x$, $>10x$ upper limit of normal (ULN)
- Aspartate aminotransferase $>3x$, $>5x$, $>10x$ ULN
- Alanine aminotransferase and/or AST $>3x$, $>5x$, $>10x$ ULN
- Alanine aminotransferase and AST $>3x$, $>5x$, $>10x$ ULN
- Total bilirubin $>2x$ ULN
- Alanine aminotransferase and/or Aspartate aminotransferase $>3x$ ULN, and total bilirubin $>2x$ ULN

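### Phase 3 safety has only an end-of-study analysis, so crude TEAE percentages and cumulative laboratory and vital-sign tables cover unequal time if conversion differs between arms

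*SAP*

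**What the plan says.** SAP 3.5 plans two safety analyses for Phase 2, one through Month 6 and one through end of study. For Phase 3, "a single analysis of safety through the end of study will be generated for Phase 3". SAP 3.4 gives the reason: "as the trial was prematurely terminated, only a single overall analysis stage will be performed for Phase 3". Protocol 3.1 had planned otherwise: "Initial Phase 3 data analyses will include a review of patient-reported clinical symptom responses, microbiological, safety, and PK data" through Month 6.

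Time on drug after Month 6 depends on culture results (Protocol 3.1.1):
- "Patients who are assessed as non-converters will discontinue study drug at the Month 6 Visit".
- Converters "will continue taking blinded study drug for 12 months after the first month that defines sputum culture conversion", to a maximum of 16 months.
- Patients with a negative Month 4 culture and no Month 5 result yet "will be presumed to be converters and will continue blinded study drug at the Month 6 Visit".

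Under SAP 3.5.1, non-serious TEAEs count through EOT and serious ones through LFU, and AESIs are monitored through LFU. Under SAP 3.5.2, the worst post-baseline CTCAE grade "will be derived from all post-baseline visits including scheduled and unscheduled". The hemoglobin categories (SAP 3.5.2) and vital-sign outliers (SAP 3.5.3) are also patient percentages over post-baseline data, with no time limit.

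Two further provisions matter. SAP 3.5.1 plans an AE overview per patient-year of exposure, with the same adjustment for SAEs, AESIs and drug-related TEAEs by SOC and PT. SAP 3.3.7 still states: "For each study phase, study drug exposure will be summarized in both a Month 6 analysis" and a final analysis.

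**The concern.** Up to Month 6 both arms follow one schedule. After that, the time over which a non-serious TEAE or a low hemoglobin value can be recorded depends on conversion, which is a post-randomization efficacy outcome. A cumulative percentage rises with observed time, so the arm that converts more would show more events even at equal risk. If epetraborole converted less than placebo, the same tables would understate its risk.

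Anemia is a pre-defined AESI (Protocol 7.9.1.2), and the hemoglobin-category tables have no exposure adjustment. By-visit means and plots after Month 6 describe a selected subset. Early termination explains a single database lock, but it does not explain dropping a data cut that can be run at that lock.

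**Working it through.** **Inputs from the documents**
- Response rates of 30% vs 10% (Protocol 8.2.4.2). They are stated for PRO response but taken from published culture conversion rates, and are used here as conversion rates.
- Non-converters: 6 months on drug.
- Converters: the first negative month is Month 1 to 4, so 13 to 16 months in total. The mean is 14.5 if these are equally likely.
- Phase 3 opened in September 2023 and the trial was terminated on 08 August 2024 (SAP 1), about 11 months later.

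**Assumed, not in the documents:** the six-month event risk, a constant hazard equal in both arms, the per-visit probabilities, and when dosing stopped after termination.

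**The plan's own figure.** The documents give no safety figure. The sample-size statement that supplies 30% vs 10% does reproduce. With 124 vs 62 patients and two-sided alpha 0.05, power is 0.897 by normal approximation and 0.907 by exact enumeration of the Miettinen-Nurminen score test, against a stated figure of approximately 90%.

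**Crude incidence.** For conversion rate c, converter time T and hazard h:

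crude = 1 − [(1 − c)·exp(−6h) + c·exp(−Th)]

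A six-month risk of 30% gives h = −ln(0.7)/6 = 0.0594 per month.

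- T = 14.5: exp(−14.5h) = 0.422. Epetraborole: 1 − (0.7×0.7 + 0.3×0.422) = 38.3%. Placebo: 1 − (0.9×0.7 + 0.1×0.422) = 32.8%. Excess = 0.2×(0.7 − 0.422) = 5.6 points.
- T = 11: exp(−11h) = 0.520. The result is 35.4% vs 31.8%, an excess of 3.6 points.
- Uniform entry over 11 months with dosing stopped at termination: excess = (0.2/11) × ∫ from 6 to 11 of [0.7 − exp(−ha)] da = (0.2/11) × 0.472 = 0.9 points. For risks of 10% and 50% it is 0.35 and 1.1 points.

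**Sensitivity at 30% vs 10% conversion**

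| Six-month risk | T = 11 | T = 13 | T = 16 |
|---|---|---|---|
| 10% | +1.5 | +2.1 | +2.9 |
| 20% | +2.7 | +3.7 | +5.0 |
| 40% | +4.2 | +5.4 | +6.9 |

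Other cases at 20% risk:
- Conversion 15% vs 10%: +0.9 to +1.2 (T = 13 to 16). Reversed, at 10% vs 15%: −0.9 to −1.2.
- Equal conversion: 0.
- Half the hazard after Month 6 (T = 16): +2.7. No hazard after Month 6: 0.
- SAEs counted to LFU: +3.3 to +4.4 (T = 13 to 16).

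**Visit-based tables.** With k0 and k1 post-baseline assessments and per-visit probability q (visits taken as independent), crude = 1 − [(1 − c)(1 − q)^k0 + c(1 − q)^k1].
- Hemoglobin, about 7 vs 14 to 17 samples, q from 1% to 5%: +1.3 to +5.6 points with full-length treatment.
- QTcF, 4 vs 5 ECGs, same q: +0.2 to +0.8 points. No ECG is scheduled between Month 6 and EOT.

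**The planned exposure adjustment.** Mean exposure at T = 14.5 is 0.7×6 + 0.3×14.5 = 8.55 vs 0.9×6 + 0.1×14.5 = 6.85 months, a ratio of 1.248. SAP 3.5.1 divides patients with an event by total exposure, not by time to first event. When the true ratio is 1, that rate ratio at T = 16 is 0.98, 0.95 and 0.90 for six-month risks of 10%, 20% and 40%. It removes most of the distortion for uncommon events and over-corrects for common ones.

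**After the fix.** With a cut at Month 6, equal hazard gives equal percentages (for example 20% vs 20%) whatever the conversion rates.

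**The case against.** The strongest reply has five parts.

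1. **AE rates are already adjusted for exposure.** This stands for AE categories, including anemia as an AESI. It does not reach the worst-grade, hemoglobin-category or vital-sign outlier tables.
2. **A common-time comparison exists.** Laboratory, vital-sign and ECG results are summarized by scheduled visit, so Months 1 to 6 can be read directly. A reader might infer that Phase 3 has no comparison over common time; the documents do not support that. What is missing is a cumulative or TEAE comparison limited to Month 6.
3. **Follow-up does not end at Month 6 for non-converters.** Every patient is due an LFU visit 84 days after the last dose, with SAEs collected and AESIs monitored to that point. This rules out the reading that only converters remain under assessment. Observed time still differs, because LFU is counted from the last dose.
4. **The largest figures may not apply.** SAP 1 reports that epetraborole was not superior in Phase 2 conversion, without rates. Thirteen to 16 months of treatment would also run past termination. A reader might infer a bias of about 5 points against epetraborole, but neither its direction nor its size is established.
5. **The choice is disclosed and safety is descriptive.** SAP 3.5 plans no hypothesis test, so no formal inference is distorted. That limits the weight of the point, but readers will still compare the percentages between arms.

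A QTcF concern might also be inferred. One extra ECG makes it negligible.

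**Conclusion.** The point holds in a limited form. Phase 3 has no Month 6 limit on crude TEAE percentages or on the cumulative worst-grade, hemoglobin-category and vital-sign outlier tables, and time at risk after Month 6 follows conversion status. The distortion can go in either direction.

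At an assumed 30% six-month risk and a 30% vs 10% conversion gap, it ranges from about 0.9 points (uniform entry, dosing stopped at termination) through 3.6 points (11-month cap) to 5.6 points (full-length treatment). Given the dates in SAP 1, the lower part of that range is more plausible if dosing stopped at termination, which the documents do not state. All these figures assume an equal constant hazard. The distortion vanishes with equal conversion or with no hazard after Month 6.

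The documents also need reconciling whatever its size. SAP 3.3.7 keeps a Month 6 analysis in each phase and SAP 3.5.1 still allows incidence rates through Month 6, while SAP 3.4 and 3.5 allow one Phase 3 analysis. SAP Section 5 does not list the dropped Phase 3 Month 6 safety review as a change from the protocol.

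**What to change.** At the single Phase 3 lock, add a data cut through each patient's Month 6 visit, or earlier discontinuation, for the TEAE, AESI, worst-grade, hemoglobin-category and vital-sign outlier tables. Name it in SAP 3.5 as the between-arm comparison. Keep the end-of-study tables as supplementary, with visits after Month 6 labelled as converters and presumed converters. Reconcile SAP 3.3.7 and the Month 6 wording in 3.5.1 with 3.4 and 3.5, and list the change in Section 5.

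The cost is a modest amount of additional output. No second lock is needed, and the Phase 2 Month 6 safety programs can be reused.

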3.5.1 Treatment-emergent Adverse Events (TEAEs)

An AE is defined as any untoward medical occurrence in a clinical investigation patient administered a pharmaceutical product, which does not necessarily have a causal relationship with this treatment. An AE can therefore be any unfavorable and/or unintended sign (including an abnormal laboratory finding), symptom, or disease temporally associated with the use of an investigational medicinal product, whether or not related to the investigational medicinal product (IMP), whether or not related to the IMP. All AEs, including observed or volunteered problems, complaints, or symptoms, are to be recorded on the appropriate eCRF. SAEs occurring from the time of informed consent through LFU will be collected. For non-serious AEs, TEAEs are defined as AEs that started from the time of the first dose of study drug through EOT; for serious AEs, TEAEs are defined as SAEs that started from the time of the first dose of study drug through LFU.

Investigators will monitor each patient for clinical and laboratory evidence for pre-defined AEs of special interest (AESIs) through LFU.

For this study, gastrointestinal intolerance, anemia, and (added prior to the Phase 3 analysis only) pneumonitis are considered AESIs. During the course of the study, additional AESIs may be identified by the Sponsor, and will be documented to support safety analyses at each analysis time point. A list of preferred terms to be included as AESIs by category will be finalized by the Sponsor prior to database lock and unblinding of each planned analysis.

AESIs related to gastrointestinal intolerance include, but are not limited to:

- *C. difficile* colitis

- Pseudomembranous colitis
- *C. difficile* test positive
- Diarrhea
- Nausea
- Vomiting

AESIs related to anemia include, but are not limited to:

- Anemia
- Aplastic anemia
- Coombs negative hemolytic anemia
- Coombs positive hemolytic anemia
- Hematocrit decreased
- Hemoglobin decreased
- Hemolysis
- Hemolytic anemia
- Intravascular hemolysis
- RBC decreased

AESIs related to pneumonitis (for Phase 3 only) included, but are not limited to:

- Pneumonitis
- Hypersensitivity pneumonitis
- Interstitial lung disease
- Pulmonary toxicity

An overview of AEs will be provided including counts and percentages of patients (and event counts) with the following:

- Any TEAEs (overall and by maximum severity)
- Any study drug related (definitely related, probably related, and possibly related) TEAEs (overall and by maximum severity)
- Any treatment-emergent AESIs (overall and by maximum severity, as well as by specific AESI category as described above)
- Any serious AEs (SAEs)
- Any TEAEs related to COVID-19
- Any treatment-emergent SAEs
- Any study drug related treatment-emergent SAEs
- Any TEAEs leading to premature discontinuation of study drug
- Any TEAEs leading to study drug interruption
- Any TEAEs of Grade 3 anemia or worse leading to study drug interruption
- Any AEs leading to death

Counts and percentages of patients will also be presented by SOC (or AESI category) and PT for each of the categories listed in the overview. Summaries of all TEAEs, all study drug related TEAEs, and all SAEs by decreasing frequency of PT for epetraborole will also be provided by treatment and overall. Based on version 25.0 or later of MedDRA, AEs reported due to COVID-19 will be appropriately coded in the listings and identifiable in the summary tables and listings by SOC and PT.

AE summaries will include the number of patients with a given AE, as well as the number of AEs themselves.

For all summaries, patients will be counted once for each AE category, SOC, or individual AE PT. For the summaries by severity grade, every patient will be counted once for each AE at the highest severity.

An overview of AEs in the format described above will be provided for key subgroups of interest, including age category, sex, geographic region and country, baseline creatinine clearance category (<60 mL/min, ≥60 mL/min to <90 mL/min, or ≥90 mL/min), and baseline BMI category (<18.5 vs ≥18.5 kg/m²).

Additionally, an overview of AEs listing all categories described above will be provided after adjusting for total patient-years of exposure. Incidence rates will be calculated as the number of patients who experienced one or more events in each category during the specific study duration (through Month 6 or overall), divided by the sum of the number of years of exposure across all exposed subjects in each treatment arm. Total years of exposure will be based on the duration of exposure (in days) calculated for each patient as defined in Section 3.3.7, divided by 365.25 days, and rounded to the nearest tenth of a year. Additional summaries of AE categories of SAEs, AESIs, and study drug related TEAEs by SOC (or AESI category) and PT adjusted for patient-years of exposure will also be generated.

Listings will be provided for all TEAEs, SAEs, TEAEs of special interest, TEAEs leading to study drug discontinuation, and TEAEs leading to death for all patients in the Safety Population. COVID-19-associated AEs will be coded as a specific preferred term in these listings.

A listing of all deaths, including the date of death and primary cause of death, will be presented for all patients in the Safety Population.

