Abbreviations: AE = adverse event; CGIC = Clinician Global Impression of Change; CGIS = Clinician Global Impression of Severity; CT = computed tomography; D = Day; ECG = electrocardiogram; EOT = End of Therapy; ET = Early Termination; FOCP = female of childbearing potential; HHC = home health care; LFU = Late Follow-up; MAC = *Mycobacterium avium* complex; NTM = Nontuberculous mycobacteria; OBR = optimized background regimen; PGIC = Patient Global Impression of Change; PGIS = Patient Global Impression of Severity; PRO = Patient-Reported Outcome; QD = once daily; QOL-B = Quality of Life-Bronchiectasis; SAE = serious adverse event; SGRQ-C = St. George's Respiratory Questionnaire for Chronic Obstructive Pulmonary Disease patients; TEAE = treatment-emergent adverse event.

^a Each patient's duration of treatment will vary depending on the timing of their MAC culture conversion; see [Section 3.1.1](#) for details.

^b Visit may be conducted in person or via HHC, if available.

^c EOT Visit/ET: Perform EOT Visit within 7 calendar days after the last dose of study drug. All reasonable efforts should be made to conduct EOT Visit in person but HHC will be supported, if needed. The EOT assessments may be performed during a regularly scheduled clinic visit if within the EOT window. Patients with clinically significant abnormal laboratory values at EOT that are deemed possibly or probably related to study drug will have repeated laboratory assessments until values return to normal or pre-study baseline values. For patients who are withdrawn from the study prior to completion, all the EOT Visit procedures will be performed at an ET Visit.

^d LFU Visit: Perform 3 months (84 days ±14 days) after the last dose of study drug. Visit may be conducted in person or via HHC, if available.

- ^e Study days are anchored to Day 1.
- ^f Physical Exam: See [Section 7.5.1.1](#); perform before the administration of study drug at the treatment visits.
- ^g Vital Signs: See [Section 7.5.1.2](#); when possible, obtain vitals after at least 5 minutes resting in a supine or sitting position.
- ^h ECGs: See [Section 7.5.1.3](#); when possible, collect ECGs after at least 5 minutes resting in a supine or semi-recumbent position.
- ⁱ Chest CTs: See [Section 7.5.1.4](#) for details, including timing of EOT CTs.
- ^j Laboratory samples (central laboratory): See details in [Section 7.5.2](#) and list of analytes in [Appendix B](#).

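### Exposure-adjusted SAE rates count events to Late Follow-up but divide by time on drug only, so the rates are overstated

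*SAP*

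**What the plan says.** - **Rate (SAP 3.5.1).** The numerator is the "number of patients who experienced one or more events in each category during the specific study duration (through Month 6 or overall"). It is "divided by the sum of the number of years of exposure across all exposed subjects in each treatment arm". The same denominator serves every category of the AE overview, and again the tables of SAEs, AESIs and drug-related TEAEs by SOC and PT.
- **Exposure (SAP 3.3.7).** In the final analysis it is "date of last confirmed treatment – date of first treatment + 1". No time after the last dose is added, and nothing stops the clock at a patient's first event.
- **Event windows (SAP 3.5.1).** For non-serious events, "TEAEs are defined as AEs that started from the time of the first dose of study drug through EOT". For serious events, "TEAEs are defined as SAEs that started from the time of the first dose of study drug through LFU". Protocol Appendix A places the LFU visit: "Perform 3 months (84 days ±14 days) after the last dose of study drug". EOT falls within 7 days of the last dose.
- **Pre-dose SAEs.** SAEs are collected from informed consent, and the overview lists any serious AE as a row separate from treatment-emergent SAEs.
- **Treatment length (Protocol 3.1.1).** Non-converters stop at Month 6. Converters continue for 12 months after the first month that defines conversion, to at most 16 months.
- **Phase 3 (SAP 3.5).** Phase 2 safety is summarised both through Month 6 and through end of study, but "a single analysis of safety through the end of study will be generated for Phase 3".

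Protocol 8.2.2 ends the TEAE period at EOT for all AEs. The SAP's extension to LFU for serious events is not listed among the changes in SAP Section 5.

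**The concern.** A rate per patient-year needs events and time drawn from the same period. Here the serious-event numerator runs about 12 weeks past the point where the denominator stops, and one row may also reach back before the first dose. Those extra weeks weigh most for patients with short exposure.

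The purpose of these tables is to make arms comparable when treatment length differs, and in this trial length depends on culture conversion and on early stopping. A rate that itself varies with treatment length at identical risk does not do that job. A second, opposite effect comes from leaving a patient's exposure in the denominator after the first event although the patient is counted once; this pulls down the rates of common events.

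**Working it through.** The documents state no AE rate, so there is no figure to reproduce.

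**1. Window covered against exposure counted (SAEs).** Ratio = (d + f)/d, where d is days on drug and f is days from last dose to LFU (84, range 70 to 98). Month 6 is Day 169 and Month 16 is Day 449 (Protocol Appendix A). Day 60 is an assumed early stop.

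| Last dose | f = 84 | f = 70 to 98 |
|---|---|---|
| Day 60 | 144/60 = 2.40 | 2.17 to 2.63 |
| Day 169 | 253/169 = 1.50 | 1.41 to 1.58 |
| Day 449 | 533/449 = 1.19 | 1.16 to 1.22 |

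This equals the rate overstatement only for rare events whose hazard is the same on and off drug (assumption). With no SAEs after stopping there would be no inflation from this source. For non-serious events f is at most 7 days.

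**2. SAE rates by arm.** Assume one constant first-event hazard L per year in both arms. With w the share of patients at each duration:

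planned rate = Σ w[1 − exp(−L(d + 84)/365.25)] / Σ w(d/365.25)

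Non-converters: d = 169. Converters: d = 365 (first negative culture at Month 1, so stop at Month 13) to 449 (first negative at Month 4, so stop at Month 16). Conversion of 30% vs 10% is the planning assumption in Protocol 8.2.4. L from 0.05 to 0.4 is assumed.

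Example with L = 0.1 and converters at 449 days:
- Epetraborole: (0.3 × 0.1358 + 0.7 × 0.0669)/(0.3 × 1.229 + 0.7 × 0.463) = 0.0876/0.693 = 0.126, which is 26% above L.
- Placebo: (0.1 × 0.1358 + 0.9 × 0.0669)/(0.1 × 1.229 + 0.9 × 0.463) = 0.0738/0.539 = 0.137, which is 37% above L.
- Ratio 0.92, where the truth is 1.00.

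Over the full range of L and converter durations the ratio is 0.90 to 0.94. With the same duration distribution in both arms it is 1.00, while the absolute rates stay biased.

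Unequal early stopping works the other way. If 20% vs 5% stop at Day 60 and the rest at Day 169 (assumption), the ratio is about 1.04.

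**3. Exposure kept after the first event (non-serious events).** Same formula with 0 in place of 84, converters at 449 days, 30% vs 10% conversion:

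| L per year | Planned/true, epetraborole | Planned/true, placebo | Arm ratio |
|---|---|---|---|
| 0.1 | 0.96 | 0.97 | 0.99 |
| 1 | 0.68 | 0.75 | 0.91 |
| 4 | 0.32 | 0.40 | 0.81 |

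The effect is small for rare events and substantial for common ones.

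**4. What time at risk repairs.** If time is counted to the first event or to the end of that row's window, the expected rate equals L in each arm under a constant hazard, and the ratio is 1.00 whatever the durations.

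Early-onset events do not follow a constant hazard. Suppose a proportion p of each arm has the event near the start, and mean exposures are E₁ and E₂. The planned ratio is (p/E₁)/(p/E₂) = E₂/E₁. With time at risk it is {p/[(1 − p)E₁]}/{p/[(1 − p)E₂]} = E₂/E₁ again. Only a common window removes the dependence on treatment length.

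**5. Rounding.** Exposure is rounded to a tenth of a year. Applied per patient, 169 days (0.463 years) becomes 0.5, which is 8% too long. Applied to an arm total, the effect is negligible.

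**The case against.** The case against is substantial on consequence and on the arm comparison.

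- **Descriptive tables.** SAP 3.5 rules out hypothesis testing for safety, and crude counts, percentages and listings stand beside these rates. Haemoglobin has its own by-visit, shift, threshold and recovery summaries. This stands, and it limits the importance of the point.
- **Superseded planning rates.** SAP Section 1 reports that Phase 2 did not show superior culture conversion and that the trial was terminated on 08 August 2024, about 11 months after Phase 3 enrolment began in September 2023. The documents do not say when Phase 3 dosing ended. If it ended near termination, calendar date would set much of the treatment length. The figures of 0.90–0.94 are therefore an illustration, not a forecast. The overstatement of absolute SAE rates needs no difference between arms and remains.
- **Pre-dose events are partly handled.** The treatment-emergent SAE row already excludes them, so only the any-serious-AE row is exposed.
- **An openly defined summary.** Patients per total patient-years is a stated descriptive measure, and preferring time to first event is partly a matter of choice. That answers the post-event exposure point in part. It does not answer a numerator and denominator that cover different periods.

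A reader might infer that an arm with more converters will look safer for nausea or haemoglobin fall because exposure after the event is kept, and that time at risk would cure this. Step 4 shows that it would not: the cause is a hazard that falls over time. A reader might also infer an 8% rounding error. The SAP sentence has total years of exposure as its subject, so rounding of the total is the more natural reading; the text only needs clarifying.

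**Conclusion.** The point holds for serious events. As written, the exposure-adjusted rates for SAEs, serious AESIs and deaths count events over a longer period than the denominator covers: 1.50 times as long for a patient stopping at Month 6, more for early stops and less for long treatment. The rates are overstated by that factor only for rare events with equal hazard on and off drug; for more frequent events, exposure kept after the first event offsets part of it. Rows that mix serious and non-serious events inherit the mismatch through their serious part.

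Distortion between arms requires different treatment durations. Under the assumptions of step 2 it is 6% to 10% in the SAE rate ratio, and it vanishes with equal durations. The documents do not support a claim that the Phase 3 comparison will be biased by a known amount or in a known direction, nor that every AE rate in these tables is materially wrong. The change should be made before Phase 3 unblinding; no efficacy conclusion or test depends on it.

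**What to change.** In SAP 3.5.1, for the exposure-adjusted rows:

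1. Count only events that start after the first dose, and match the denominator to the numerator's window. Run time from first dose to first event in that category, or otherwise to LFU or last contact for SAE and death rows, and to EOT for non-serious rows. For rows that mix serious and non-serious events (any TEAE, AESI), cut both numerator and denominator at EOT; later serious events remain visible in the SAE rows.
2. Add the through-Month-6 AE overview for Phase 3, as in Phase 2. This is what addresses early-onset events. SAP 3.3.7 already defines Month 6 exposure for each phase.
3. State that rounding applies to the arm total or the final rate, not to each patient.
4. List the LFU window for serious TEAEs in SAP Section 5 as a change from Protocol 8.2.2.

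Cost: SAP wording, a modified denominator derivation and one extra descriptive table set. No new data are needed.
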